4.4 Withdrawal Criteria

Participation of a patient in this study may be discontinued for any of the following reasons:

- Withdrawal of consent or request for discontinuation from the study for any reason;
- Occurrence of any medical condition or circumstance that exposes the patient to substantial risk and/or does not allow the patient to adhere to the requirements of the protocol;
- Any SAE, clinically significant AE, severe laboratory abnormality, intercurrent illness, or other medical condition which indicates to the Investigator that continued participation is not in the best interest of the patient;
- Pregnancy;
- Use of prohibited concomitant medication;
- Patient failure to comply with protocol requirements or study-related procedures; or
- Termination of the study by the Sponsor or the regulatory authority.

For patients who discontinue early from the study, the Investigator is responsible to ensure all safety assessments and final follow-up assessments scheduled for the end of study (EOS) visit, including follow-up for unresolved AEs (including SAEs), are completed prior to patient discontinuation. If the patient does not return for a scheduled visit, the Investigator must make every effort (documented telephone calls and registered letter, as allowed) to contact the patient. Patients will be deemed as lost-to-follow-up once the Investigator has completed a minimum of 3 telephone calls followed by a certified letter (as allowed) to the last known address of the patient or next of kin, as appropriate, with no response obtained. Attempts to contact the patient must be made and documented in the patient's medical records.

Patients who are consented but do not meet eligibility criteria will be considered screen failures. Patients withdrawn for safety reasons will not be replaced.

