4.3.1 Criteria for Discontinuation of Dosing in Individual Patients

Patients will be discontinued from dosing but will continue to be followed in the study if they experience any of the following:

- \geq Grade 3 (CTCAE v5.0) AE or clinically significant laboratory abnormality considered related to study drug;
- \geq Grade 3 (CTCAE v5.0) infusion reaction in the first 24 hours post-infusion;
- \geq Grade 2 (CTCAE v5.0) cytokine release syndrome;
- \geq Grade 2 skin-related AEs;
- Severe anaphylactic reaction, including bronchospasm; and/or
- Progression to acute respiratory distress syndrome.

For any patient who prematurely discontinues from study treatment, the reason and date of discontinuation will be documented in the electronic case report form (eCRF) and the patient should continue study visits and procedures as outlined in the Schedules of Procedures ([Appendix A](#)).

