9.2 Statistical Methods

9.2.1 Analysis of Efficacy

9.2.1.1 Primary efficacy endpoint

The time to achieve a ≥ 2 -point increase in the NIAID 8-point ordinal scale from baseline by Day 29 will be analyzed using the Cochran-Mantel-Haenszel (CMH) test adjusting for the baseline NIAID 8-point ordinal scale. The NIAID 8-point ordinal scale will be assessed daily while the patient is hospitalized. If the patient remains hospitalized, the scale will also be assessed on Days 15 and 29. Any patient in the ITT Population with a missing primary endpoint result will be considered as a non-responder. The point estimates of the time to achieve a ≥ 2 -point increase will be presented by treatment arm together with their 95% confidence intervals. The CMH odds ratio, associated 95% confidence interval, and p-value will also be presented.

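### Section 4.4 lets a prohibited medicine or non-compliance end study follow-up, not only dosing, without asking for the outcomes still due at Days 15, 29 and 60

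*Combined protocol and SAP*

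**What the plan says.** Two sections of the protocol deal with patients who stop early.

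- Section 4.3.1 concerns dosing: "Patients will be discontinued from dosing but will continue to be followed in the study". Its closing paragraph extends this to anyone who stops study treatment prematurely: "the patient should continue study visits and procedures as outlined in the Schedules of Procedures".
- Section 4.4 concerns the study itself: "Participation of a patient in this study may be discontinued for any of the following reasons". The reasons include "Use of prohibited concomitant medication" and "Patient failure to comply with protocol requirements or study-related procedures". For patients who leave, "the Investigator is responsible to ensure all safety assessments and final follow-up assessments scheduled for the end of study (EOS) visit" before exit, including follow-up of unresolved adverse events. Nothing is requested on the efficacy scale or vital status at the later time points.

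Section 9.1 defines the ITT Population as every randomized patient. Section 9.2.1.1 then states: "Any patient in the ITT Population with a missing primary endpoint result will be considered as a non-responder". Section 9.2.1.2 applies the method of the primary endpoint to mortality, discharge, progression and the other tested secondary endpoints. Section 3.1 sets efficacy assessment at Days 15 and 29 and safety follow-up to Day 60.

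**The concern.** Using a prohibited medicine or missing procedures is a departure from the protocol. It does not make the patient's later outcome unobtainable. If such a patient is taken out of the study, an outcome that could have been recorded is replaced by an imputed one. Only two infusions are given, on Days 1 and 8, so removal after Day 8 withholds no study drug and only ends data collection.

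The imputation also has no clear meaning across endpoints. On this scale 1 is death and 8 is full activity at home, so a 2-point increase is improvement and non-response is the unfavourable result. For mortality, a 2-point decrease or progression, the plan does not say what a non-responder is. If it means a patient without the event, someone removed who later dies counts as a survivor.

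Section 8.3 adds to this. Progression of COVID-19 is treated as efficacy data and is not reported as a serious adverse event unless it is drug-related or fatal. Non-fatal worsening after exit may therefore be recorded nowhere.

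**Working it through.** **Reading the two sections together**

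- After stopping study drug only (4.3.1), visits and procedures continue, so NIAID grade, vital status and safety are all still collected.
- After leaving the study (4.4), end-of-study and safety assessments are brought forward and unresolved adverse events are followed. Day 15 and Day 29 efficacy status and safety to Day 60 are not requested.
- Adverse events appear in both sections, so follow-up continues under one and may end under the other.

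**Which patients are affected.** A patient who has already gained 2 points has a primary result and is not recoded. A Day 15 value is lost only if exit comes before Day 15. For a patient whose baseline grade is 5 or lower, discharge alone (grade 7 or 8) is a gain of at least 7 − 5 = 2. For such patients the primary endpoint is exposed only to exits before discharge. Mortality by Day 29 and safety to Day 60 stay exposed after discharge.

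**Arm size.** Section 9.2.5 gives 4 + 14 + 4 + 16 = 38, which reproduces the stated total. Section 3.1 gives 2 + 7 + 2 + 8 = 19 per arm.

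**Shift in the observed response rate**

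- Ceiling, if every removed patient would have responded: 1/19 = 5.3 points for one and 2/19 = 10.5 points for two.
- Expected shift for w patients removed from one arm, unrelated to outcome, with true response p: p × w/19. For w = 2, p = 0.60 gives 0.60 × 2/19 = 6.3 points and p = 0.90 gives 0.90 × 2/19 = 9.5 points.
- The second formula gives each removed patient the full chance p of a later response. That suits exit soon after randomization and is generous for later exit.

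**Effect on the test.** These figures are illustrations. They use exact enumeration with 19 per arm, the endpoint reduced to responder or not by Day 29, a single-stratum Mantel-Haenszel chi-square at two-sided 0.05, and removed patients fixed as non-responders.

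- Equal true response of 60% to 90% in both arms: the chance of nominal significance is 3.6% to 5.0% with none removed, and 5.3% to 9.5% with exactly two removed from one arm.
- True response of 60% on placebo and 85% on F-652: power is 41% with none removed, 27% with two removed per arm, and 16% with two removed from the F-652 arm only.

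The response rates and numbers removed are assumptions; the documents state neither.

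**The case against.** The strongest case for leaving the text alone has five parts.

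- **Withdrawal is optional.** Section 4.4 says participation may be discontinued, and decisions are made blinded. This is true, but no criterion guides the choice at about 10 sites, so whether the outcome is collected depends on local judgement.
- **Safeguards exist.** End-of-study assessments precede exit. Section 8.4 requires a patient with a serious adverse event to be followed until it subsides, becomes chronic or stabilizes, or the patient dies. Section 8.3 requires fatal progression in the reporting period to be recorded. This stands: safety data are curtailed, not wholly lost. None of these provisions asks for efficacy status at Days 15 and 29.
- **The adverse-event reason is conditional.** It applies when the investigator judges that staying in is against the patient's interest. This stands, and the point here is confined to prohibited medicines and non-compliance.
- **The study is exploratory.** It has 38 patients and no power calculation. This limits the weight of the point, but each lost outcome counts for more in so small a trial.
- **Relevant text is unavailable.** The prohibited-medication list (Section 5.6.1) and the schedule in Appendix A are not in the available text, so it cannot be seen how often the rule would apply or what the end-of-study visit collects.

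A reader might infer that the patients removed are mainly those who are worsening and receive other COVID-19 treatment, so that the ITT comparison is biased. The documents do not support this. Antivirals are allowed as standard of care (Sections 3.1 and 5.1), and the list of what is prohibited cannot be seen. A patient who is worsening and would not have gained 2 points is a non-responder either way, so recoding that patient moves the primary rate by zero. A reader might also infer that outcomes at all three time points are discarded and scored as non-response. Data before exit are kept, and the non-responder rule does not reach Day 60 safety.

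**Conclusion.** The point holds as a gap between two rules with a concrete consequence. Sections 4.3.1 and 4.4 lead to opposite follow-up, and for prohibited medicines and non-compliance Section 4.4 can turn an obtainable Day 29 outcome into an imputed one. The effect on an arm's response rate is at most 5.3 points per removed patient and at most 10.5 for two. The 6.3 to 9.5 points for two rest on an assumed 60% to 90% response and removal unrelated to outcome, in one arm only. Removal balanced across arms would mainly cost power. The documents give no withdrawal rate, so neither the size nor the direction of any bias is established. This is a cheap improvement to the plan; it does not show that the planned analysis is invalid.

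**What to change.** Reconcile Sections 4.3.1 and 4.4 by separating data collection from dosing, without changing any rule on when dosing stops. Possible wording for Section 4.4:

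> Use of a prohibited medicine or non-compliance is recorded as a protocol deviation and intercurrent event and is not by itself a reason to end follow-up. NIAID grade and vital status are collected at Days 15 and 29, and safety to Day 60, unless the patient withdraws consent to follow-up.

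Leave the investigator's best-interest withdrawal and the pregnancy rule in Section 8.5 in place. The Per Protocol Population in Section 9.1 already deals with major deviations, so the analysis does not need these patients removed.

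In the SAP, state for each tested endpoint how a missing result is scored, in particular for mortality, a 2-point decrease and progression, and add a sensitivity analysis to the non-responder rule.

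The cost is amendment wording and a few more follow-up contacts. The sample size stays at 38.

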5 STUDY TREATMENTS

5.1 Treatment Groups

The study drug will be administered only to patients who have given informed consent.

The patients will be randomly assigned to F-652 or placebo treatment in a 1:1 ratio in a blinded manner. Treatment will begin on Day 1 following randomization. All patients will receive available supportive and antiviral therapies as standard of care.

5.3 Randomization and Blinding

Patients will be randomized in a 1:1 ratio in a double-blind manner to receive F-652 or placebo.

An independent statistician from Medpace Inc., hereinafter Medpace, will generate the randomization schedule. Patients meeting eligibility criteria will be randomized on Day 1, following screening, in a 1:1 ratio to F-652 or placebo, respectively. Patients will be assigned a randomization number and treatment assignment according to the randomization schedule. This randomization schedule will be maintained by the investigative site pharmacist until it is appropriate to break the blind. The Investigator, investigative site personnel (except site-designated pharmacist and dedicated assistant), study monitors, vendors, Sponsor, and Medpace will remain blinded to treatment assignment.

Details of the emergency unblinding procedures are given in Section 5.4.

5.4 Breaking the Blind

Individual treatment assignments may be unblinded when immediate knowledge of the treatment assignment is needed to optimize the clinical management of the patient. The Investigator should contact the Medical Monitor to discuss the event prior to unblinding. In the event this is not possible, the Investigator should contact the Medical Monitor as soon as possible to discuss the event.

Randomization assignments will be prepared by the independent statistician and provided to the investigative site pharmacist to enable emergency code break procedures for individual patients without compromising the blind of the study. Documentation of the blind break, including the patient's identification, reason for breaking the blind, and the date and time of breaking the blind, must be retained in the patient's source documents at the sites in such a way as to avoid unblinding the treatment assignment to other site or Sponsor blinded personnel.

5.5 Drug Supplies

5.5.1 Formulation and Packaging

The lyophilized formulation of F-652 (5 mg/vial) will be provided to the investigative sites for patients' use. It is presented as a white or yellowish cake in a sterile 3 mL glass vial. The composition of the study drug is listed in Table 2.

5.5.3 Study Drug Administration

F-652 will be administered, based on the patient's most recent weight, at a dose [REDACTED] IV on Days 1 and 8. Placebo vehicle will be identical in appearance to the study drug and will be administered IV on Days 1 and 8. If the patient is discharged from the site prior to Day 8, they will return for an outpatient visit to receive the second IV infusion and remain at the site for an approximate 2-hour observation period. [REDACTED]
[REDACTED]
[REDACTED]

The definitions and management of infusion related reactions are described in [Appendix C](#).

5.5.4 Treatment Compliance

Administration of the study drug will be performed by the investigative site staff and supervised by the Investigator or Sub-Investigator.

Details of the date and time when the study drug is administered, along with any deviation from the procedure described in this protocol, will be recorded in the patient's source documents and the eCRF.

Product technical complaints should be reported to the Sponsor. A product complaint is any report or complaint about a potential or alleged failure of the Sponsor's product to meet any of its quality specifications. These complaints may or may not represent a potential risk to the patient.

Product technical complaints may include:

- Quality defects as described in [Section 5.5.2](#) and temperature excursions;
- Defects of containers and external wrappings; or
- Defects of labeling and packaging leaflets.

6 STUDY PROCEDURES

Study procedures will follow the Schedule of Procedures ([Appendix A](#)).

7 EFFICACY ASSESSMENTS

7.1 Efficacy Endpoints

7.1.1 Primary Efficacy Endpoint

The primary efficacy endpoint is the time to achieve a ≥ 2 -point increase in the National Institute of Allergy and Infectious Diseases (NIAID) 8-point ordinal scale from baseline by Day 29.

The NIAID 8-point ordinal scale includes the following grades:

1. Death;
2. Hospitalized, on invasive mechanical ventilation or extracorporeal membrane oxygenation;
3. Hospitalized, on non-invasive ventilation or high-flow oxygen devices;
4. Hospitalized, requiring supplemental oxygen;
5. Hospitalized, not requiring supplementation oxygen – requiring ongoing medical care (COVID-19 related or otherwise);
6. Hospitalized, not requiring supplemental oxygen – no longer requires ongoing medical care;
7. Not hospitalized, limitation on activities and/or requiring home oxygen; and
8. Not hospitalized, no limitations on activities.

7.1.2 Secondary Efficacy Endpoints

The secondary efficacy endpoints, listed in hierarchical order, include the following:

- Time to achieve a ≥ 2 -point decrease in the NIAID 8-point ordinal scale;
- Length of hospital stay from first dosing (Day 1) and percentage of patients who have recovered and been discharged from the hospital by Days 15 and 29;
- Mortality rate by Days 15 and 29;
- Proportion of patients with a ≥ 2 -point increase in the NIAID 8-point ordinal scale from baseline to Days 15 and 29;
- Alive and respiratory failure free days by Days 15 and 29;
- Percentage of patients progressed to severe/critical disease by Day 15; and
- Occurrence of any new infections during the study by Day 29.

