3 STUDY DESCRIPTION

3.1 Summary of Study Design

This is an interventional, multicenter, 2-arm, parallel-group, randomized, double-blind, placebo-controlled, dose-escalation, safety and efficacy study of F-652 treatment versus placebo in patients aged 18 years or older with a COVID-19 diagnosis confirmed by polymerase chain reaction (PCR). Eligible patients will have moderate to severe COVID-19 symptoms and will be hospitalized. Figure 1 provides an overview of the study design.

AE = adverse event; COVID-19 = coronavirus disease 2019; ECG = electrocardiogram; NIAID = National Institute of Allergy and Infectious Diseases; PCR = polymerase chain reaction; PD = pharmacodynamic(s); SAE = serious adverse event; SARS-CoV-2 = severe acute respiratory syndrome coronavirus 2; TEAE = treatment-emergent adverse event.

The study plans to include 4 cohorts (see [Table 1](#)), with enrolled patients being randomized 1:1 in a blinded manner on Day 1, following screening, to F-652 or placebo as follows:

- Cohort 1 (sentinel cohort): Four patients will receive either [REDACTED] or placebo. Two patients will receive F-652 and 2 patients will receive placebo. Upon completion of sentinel dosing (7 days after last patient last dose), the Data Monitoring Committee (DMC) will evaluate the safety and tolerability data of the sentinel patients and determine if it is acceptable to dose the remaining patients in this dosing group in Cohort 2.
- Cohort 2: Fourteen patients will receive either [REDACTED] or placebo. Seven patients will receive F-652 and 7 patients will receive placebo. Upon completion of Cohort 2, the DMC will convene and review all available safety data to determine if the study can proceed to the next dose level.

- Cohort 3 (sentinel cohort): Four patients will receive either [REDACTED] or placebo. Two patients will receive F-652 and 2 patients will receive [REDACTED]. Upon completion of sentinel dosing (7 days after last patient last dose), the DMC will evaluate the safety and tolerability data of the sentinel patients and determine if it is acceptable to dose the remaining patients in this dosing group in Cohort 4. [REDACTED]
- Cohort 4: Sixteen patients will receive either [REDACTED] or placebo. Eight patients will receive F-652 and 8 patients will receive placebo. [REDACTED]

Table 1. Dosing Strategy

Cohort	Number of Patients	Dosing
1 (sentinel)	4	[REDACTED]
2	14	[REDACTED]
3 (sentinel)	4	[REDACTED]
4	16	[REDACTED]

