9.2.1.2 Secondary efficacy endpoints

The time to achieve a ≥ 2 -point decrease in the NIAID 8-point ordinal scale, proportion of patients with a ≥ 2 -point increase in the NIAID 8-point ordinal scale from baseline to Days 15 and 29, mortality rate by Days 15 and 29, percentage of patients who have recovered and been discharged from the hospital by Days 15 and 29, and percentage of patients progressed to severe/critical disease by Day 15 will be analyzed using the same method as described for the primary efficacy endpoint in Section 9.2.1.1.

The number of alive and respiratory failure free days by Days 15 and 29, the length of hospital stay from first dosing (Day 1) to discharge by Days 15 and 29, and occurrence of any new infections during the study by Day 29 will be summarized using descriptive statistics.

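### The first-listed secondary endpoint, a fall of at least 2 NIAID points, does not count intubation for a patient who enters at grade 3 and would not count death for one who enters at grade 2; how much this matters depends on redacted entry criteria.

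*Combined protocol and SAP*

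**What the plan says.** Section 7.1.2 introduces its list with "The secondary efficacy endpoints, listed in hierarchical order, include the following", and the first item is "Time to achieve a ≥ 2 -point decrease in the NIAID 8-point ordinal scale". The synopsis gives the same list.

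Section 7.1.1 prints the scale. Grade 1 is death. The next two grades are "2. Hospitalized, on invasive mechanical ventilation or extracorporeal membrane oxygenation" and "3. Hospitalized, on non-invasive ventilation or high-flow oxygen devices". Grade 4 is hospitalized on supplemental oxygen, and the top is "8. Not hospitalized, no limitations on activities". Higher is better, so a decrease is worsening.

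Section 9.2.1.2 assigns "The time to achieve a ≥ 2 -point decrease in the NIAID 8-point ordinal scale" the same analysis as the primary endpoint, which is a CMH test adjusted for baseline grade (section 9.2.1.1). No visible section adds a rule that intubation or death counts as worsening whatever the starting grade. The item also names no reference grade and no time limit, whereas the primary endpoint is measured from baseline to Day 29.

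On who can enter, section 3.1 says "Eligible patients will have moderate to severe COVID-19 symptoms and will be hospitalized". The detailed criteria are redacted.

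**The concern.** A fixed 2-point fall needs two grades of room below the starting grade, and this scale has little room near the bottom. A patient who enters on high-flow oxygen or non-invasive ventilation and is then intubated is scored as not having worsened. A patient who enters already intubated could die without having an event.

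The endpoint leads the secondary list and is the plan's main measure of deterioration. Section 8.3 adds to the concern. It keeps COVID-19 progression out of SAE reporting, unless it is fatal or judged drug-related, on the ground that efficacy endpoints will capture it. For a non-fatal intubation from grade 3, the leading deterioration endpoint does not.

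**Working it through.** **1. Which later grades count.** The rule is: event if baseline grade minus later grade is at least 2. The inputs are the grades in section 7.1.1.

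| Baseline grade | Later grades that count | Intubation (2) counts? | Death (1) counts? |
|---|---|---|---|
| 6 | 1, 2, 3, 4 | yes (6 − 2 = 4) | yes |
| 5 | 1, 2, 3 | yes (5 − 2 = 3) | yes |
| 4 | 1, 2 | yes (4 − 2 = 2) | yes |
| 3 | 1 | no (3 − 2 = 1) | yes (3 − 1 = 2) |
| 2 | none | already at grade 2 | no (2 − 1 = 1) |

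**2. Size for grade 3.** The trial has 4 + 14 + 4 + 16 = 38 patients, with 2 + 7 + 2 + 8 = 19 per arm. The plan gives no baseline distribution and no event rates, so the shares below are assumptions. Uncounted intubations = 38 × share at grade 3 × probability of being intubated and surviving.

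| Share at grade 3 | 10% intubated, survive | 30% intubated, survive |
|---|---|---|
| 0% | 0 | 0 |
| 10% | 0.4 | 1.1 |
| 30% | 1.1 | 3.4 |
| 50% | 1.9 | 5.7 |

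The range is 0 to about 6, summed over both arms. One patient is 1/19 = 5.3 percentage points of an arm, but uncounted events split evenly between arms leave the difference unchanged. A net imbalance of one patient moves it by 5.3 points, and of two by 2/19 = 10.5 points.

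**3. Size for grade 2.** With an assumed 0-20% entering at grade 2 and 20-40% mortality among them, uncounted deaths run from 0 to 38 × 0.20 × 0.40 = 3.0.

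**4. Effect on the CMH test.** Here the event is treated as present or absent by Day 29. The statistic is (ΣA − ΣE)²/ΣV. Per stratum, A is the number of active-arm events, E = n₁m/n and V = n₁n₂m(n − m)/[n²(n − 1)], where m is the total events. A stratum with no possible events has m = 0, so it adds nothing to A, E or V.

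An invented example has strata of 1/7 v 3/7 and 1/8 v 2/8:
- ΣA = 2
- ΣE = 2 + 1.5 = 3.5
- ΣV = 0.769 + 0.650 = 1.419
- Statistic = 2.25/1.419 = 1.585

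Adding a stratum of 0/4 v 0/4 leaves it at 1.585. Information is lost, but the comparison is not shifted.

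**5. What else would pick up the event.**
- Mortality by Days 15 and 29 (third in the list) counts every death, but not patients who are intubated and survive.
- Days alive without respiratory failure (fifth) should reflect intubation, but section 9.2.1.2 only summarizes them, and respiratory failure is not defined in the visible text.
- Progression to severe or critical disease (sixth) is tested, but it stops at Day 15 and is likewise undefined in the visible text.

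**6. Reference grade.** A patient who goes from 4 to 7 and is readmitted at 5 has fallen 2 points from the previous grade but stands 1 point above baseline. Baseline is the natural reading, because the analysis is the primary's and adjusts for baseline grade. This is a wording gap only.

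**The case against.** The strongest objection is relevance. Nothing visible shows that patients at grade 3 or grade 2 can enrol. Several features suggest a population not intubated at entry: progression to critical disease is an outcome, progression to acute respiratory distress syndrome stops dosing (section 4.3.1), vital signs are taken seated (section 8.9), and each patient gives written consent (section 11.3). None of these is proof. The objection stands to this extent: the grade 2 half may have no effect, and the grade 3 half is conditional.

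Second, a reader might infer that the trial could miss deaths or intubations altogether. The documents do not support that. Deaths have their own endpoint, and oxygen delivery method is recorded daily (section 8.12). The gap lies in what one endpoint counts.

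Third, a reader might infer that the comparison is biased, or that a formal testing hierarchy is compromised. Neither follows. Stratifying by baseline grade compares like with like, and no alpha or gatekeeping rule is attached to the ordering in the visible text. The study is described as exploratory, and its sample size does not rest on a power calculation.

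Finally, a symmetric 2-point rule is a legitimate choice. The alternative counts the one-point fall from 3 to 2 but not the one from 4 to 3. That is true. However, invasive ventilation already counts from grades 4 to 6 and death from grades 3 to 6, so the change makes those two outcomes count from every starting grade from which they can newly occur.

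**Conclusion.** The point holds in a limited form. It is certain from the printed scale that the endpoint does not count intubation from grade 3 and would not count death from grade 2. The practical size is not known. It is 0 to about 6 uncounted intubations over both arms, on assumed shares of 0-50% at grade 3 and 10-30% intubated and surviving. It is zero if no grade 3 patients enrol.

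The main cost is sensitivity in a small trial's leading deterioration endpoint. The lower-ranked endpoints are a partial backstop, but none tests intubation through Day 29. Since section 8.3 relies on efficacy endpoints to capture non-fatal progression, closing the gap is worthwhile. It is a cheap improvement and not an error that threatens the trial's conclusions.

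**What to change.** In the synopsis, section 7.1.2 and section 9.2.1.2, define deterioration as the first of the following, by Day 29:
- a fall of at least 2 points from baseline;
- new grade 2 in a patient not at grade 2 at baseline;
- death from any baseline grade.

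Report the plain fall of at least 2 points from baseline as a sensitivity analysis. Naming baseline and Day 29 also closes the reference-grade gap.

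Qualifying grades become {1} from baseline 2 and {1, 2} from baseline 3. Scoring from grades 4 to 6 is unchanged, and nothing changes if no grade 2 or 3 patients enrol.

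The cost is wording. Grades are already assessed daily in hospital, and section 9.2.3 leaves full technical detail to an analysis plan finalized before database lock. The downside is that the endpoint becomes a small composite and no longer mirrors the primary endpoint.
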